# 7. DETERMINATION OF SAMPLE SIZE

Based on a Chi square test at 2-sided significance level of 0.05, a total of 96 participants (32 per treatment group) will provide at least 80% power to show pairwise superiority of etrasimod 2 mg to placebo in the primary endpoint assuming 5% remission rate in the placebo group and a 31.5% remission rate in the etrasimod 2 mg group. The assumptions are based on the results from the completed Phase 2 Study APD334-003. Sample size is calculated using the EAST® software.

The actual sample size will be smaller than original planned because this study will be early discontinued in agreement with PMDA consultation.

Document: \quintiles.net\enterprise\Apps\sasdata\SASb\SAS\Arena\APD334\RZA28116\Biostatistics\Documenta

tion\SAP\503-Final SAP v2.0\APD334-203\_SAP\_Final v2.0-20231120\_clean.docx

Author: PPD Version Number: 2.0

Version Date: 20Nov2023

Template No.: CS\_TP\_BS016 Revision 7 Reference: CS\_WI\_BS005

Effective Date: 01Nov2021

<sup>e Not applicable for OCT/PFT

f Applicable for OCT/PFT

**IOVIA** 

Page 25 of 70

# 8. STATISTICAL CONSIDERATIONS

# 8.1. Multicenter Studies

This study will be conducted by multiple investigators at multiple centers in Japan.

Randomization to treatment groups is stratified by:

- Naïve to biologic or JAK inhibitor therapy at study entry (Yes or No)
- Baseline corticosteroid use (Yes or No)
- Baseline disease activity (MMS: 4 to 6 or 7 to 9)

Data from all sites will be pooled and statistical analyses will not be adjusted for investigational site.

# 8.2. Adjustments for Covariates and Factors to be Included in Analyses

Not applicable.

# 8.3. Missing Data

Missing adverse event (AE) relationship to study treatment and AE seriousness will be imputed as described in Section 18.1.1.2 and Section 18.1.3, respectively. Partial or missing AE start dates, concomitant medication (CM) start dates, and hospitalization dates will also be imputed as described in APPENDIX 2. No other missing safety data will be imputed.

Missing efficacy data will be handled as described in Sections 16.1.2, 16.2.2, 16.3.2. In the primary analysis of the primary endpoint and main analyses of all binary responder-type endpoints, all participants with missing data, regardless of reason for missingness, will be considered as non-responders. In the main analysis of continuous or score endpoints, such as biomarker measures and health-related quality of life measures, participants with missing data will be analysed with their observed data only, a mixed-effect model with repeated measures or analysis of covariance (ANCOVA).

# 8.4. Multiple Comparisons/ Multiplicity

There is no hypothesis to be tested and adjustment for multiplicity.

Document: \quintiles.net\enterprise\Apps\sasdata\SASb\SAS\Arena\APD334\RZA28116\Biostatistics\Documenta

tion\SAP\503-Final SAP v2.0\APD334-203\_SAP\_Final v2.0-20231120\_clean.docx

Author: PPD Version Number: 2.0

Version Date: 20Nov2023

Template No.: CS\_TP\_BS016 Revision 7 Reference: CS\_WI\_BS005

Effective Date: 01Nov2021

Page 26 of 70

# 8.5. Subgroups Analysis

The following subgroups will be assessed for the primary and secondary endpoints using primary method described in Section 16.1.3 on FAS with Baseline MMS 5 to 9:

- Sex (Female or Male)
- Age (≤ or > Median, < or ≥ 65)

- Baseline oral corticosteroid usage (Yes or No)
- Naïve to biologic or JAK inhibitor therapy at study entry (Yes or No)
- Baseline disease activity Actual MMS (4 to 6, 7 to 9)
- Actual Baseline MMS (5 to 7, 8 to 9)
- Baseline fecal calprotectin (≤ or > Median)
- Baseline high-sensitivity C reactive protein (≤ or > Median)
- Baseline Total Mayo score (≤ or > 8)
- Duration of UC (≤ or > Median)
- Extent of disease (Proctosigmoiditis/Left sided colitis, Pancolitis, Proctitis as reported on the eCRF)
- Proctitis (Yes or No, based on central read)
- Prior UC treatment of oral 5-aminosalicylic acid (5-ASA) only (Yes or No)
- Prior UC treatment failure of oral 5-ASA only (Yes or No)
- Number of prior biologic or JAK inhibitor therapies (1 or > 1)
- Prior UC treatment failure of antitumor necrosis factor alpha (anti-TNFα) (Yes or No)

Additional subgroups may be assessed, if deemed necessary. The medians will be derived based on FAS with baseline MMS 5 to 9 for all subgroups cut at median. It should be noted that the study was not designed to detect treatment differences with high statistical power within subgroups. If any subgroup includes < 5% of all participants, no inferential statistics will be generated.

Actual stratum at baseline will be used for all subgroup analyses.

Forest plots of the overall analysis set and all subgroups will be presented for the primary endpoint. Inference from the model described in Section 16.1.3 will be used and differences in remission percentages along with 95% CIs will be displayed.

Document: \quintiles.net\enterprise\Apps\sasdata\SASb\SAS\Arena\APD334\RZA28116\Biostatistics\Documenta

tion\SAP\503-Final SAP v2.0\APD334-203\_SAP\_Final v2.0-20231120\_clean.docx

Author: PPD Version Number: 2.0

Version Date: 20Nov2023

Template No.: CS\_TP\_BS016 Revision 7 Reference: CS\_WI\_BS005

Effective Date: 01Nov2021

Page 27 of 70

# 9. OUTPUT PRESENTATIONS

APPENDIX 1 shows conventions for presentation of data in outputs.

#### 10. DISPOSITION AND PROTOCOL DEVIATIONS

All participants who provide informed consent will be accounted for in this study.

# 10.1. Disposition

Inclusion criteria not met and exclusion criteria met will be listed.

Among the randomized participants, the number and percent of participants who completed/discontinued treatment, reasons off treatment, the number and percent of participants who completed/discontinued the study, reasons off study, and the number of participants who continue to APD334-303 will be summarized.

The number and percent of participants in each analysis set will be summarized for all randomized participants. An additional summary of the number of participants screened, the number of screen-failed participants, and reason for screen failure will be presented for all screened participants. A listing of participants whose blind was broken will be provided.

The number of participants whose visit was impacted by the coronavirus disease 2019 (COVID-19) pandemic per eCRF will also be summarized by nominal visit.

Additionally, a summary of missing endoscopy regardless of reason and missing endoscopy due to visit impacted by the COVID-19 pandemic will be presented by visit.

## 10.2. Protocol Deviations

During site monitoring, protocol deviations are graded as Critical, Major or Minor.

According to ICH E3 and ICH E3(R1), important protocol deviations are a subset of protocol deviations that might significantly affect the completeness, accuracy, and/or reliability of the study data or that might significantly affect a subject's rights, safety, or well-being (ICH 1995, ICH 2012). For example, important protocol deviations might include enrolling participants in violation of key eligibility criteria designed to ensure a specific subject population

\\quintiles.net\enterprise\Apps\sasdata\SASb\SAS\Arena\APD334\RZA28116\Biostatistics\Documenta Document

tion\SAP\503-Final SAP v2.0\APD334-203\_SAP\_Final v2.0-20231120\_clean.docx

Version Number: 2.0 Author: PPD

> Version Date: 20Nov2023

Template No.: CS\_TP\_BS016 Revision 7 Reference: CS\_WI\_BS005

Effective Date: 01Nov2021

Page 28 of 70

or failing to collect data necessary to interpret primary endpoints, as this may compromise the scientific value of the study.

During the review of all reported deviations, important deviations related to study inclusion or exclusion criteria, conduct of the study, patient management or patient assessment will be identified. Where relevant the importance of a potentially important protocol deviations will be assessed in the context of the study's estimands to evaluate potential impact.

All important protocol deviations will be summarized for the FAS in the following categories in descending frequency in the etrasimod 2 mg group.

All protocol deviations will be listed, including whether a deviation was impacted by the COVID-19 pandemic (Yes or No). Protocol deviation categories include but are not limited to the following:

- Informed Consent
- Eligibility and Entry Criteria
- Concomitant Medication
- Laboratory Assessment
- Study Procedures
- Serious Adverse Event
- Randomization
- Visit Schedule
- Investigational Product Compliance
- Efficacy
- Administrative
- Source Document
- Regulatory or Ethics Approvals
- Other

Important protocol deviations will also be summarized by whether they were impacted by the COVID-19 pandemic (Yes or No).

# 11. DEMOGRAPHIC AND OTHER BASELINE CHARACTERISTICS

The following demographic and baseline characteristics will be summarized for the FAS.

Document: \quintiles.net\enterprise\Apps\sasdata\SASb\SAS\Arena\APD334\RZA28116\Biostatistics\Documenta

tion\SAP\503-Final SAP v2.0\APD334-203\_SAP\_Final v2.0-20231120\_clean.docx

Author: PPD Version Number: 2.0

Version Date: 20Nov2023

Template No.: CS\_TP\_BS016 Revision 7 Reference: CS\_WI\_BS005

Effective Date: 01Nov2021

Page 29 of 70

- Age on consent (years)
- Sex (Male or Female)
- Woman of childbearing potential (Yes or No)
- Race
- Ethnicity
- Height (cm)
- Weight (kg)
- Body mass index (BMI) (kg/m²)
- Alcohol consumption (Yes or No)
- Caffeine consumption (Yes or No)
- Tobacco use (Yes or No)

The following Baseline characteristics related to UC will be summarized:

- Extent of disease (Proctosigmoiditis/Left-sided colitis, Pancolitis, Proctitis reported on the Ulcerative Colitis
  History electronic case report form [eCRF], and Proctitis reported from central reader review)
- Baseline MMS
- Baseline rectal bleeding (RB) subscore
- · Baseline stool frequency (SF) subscore
- Baseline endoscopic score
- Baseline Physician's Global Assessment (PGA)
- Baseline TMS
- Duration of UC (years)
- Any acute exacerbations within past 12 months (Yes or No), including the number of acute exacerbations among those with any acute exacerbation = Yes
- Colonoscopy within past 12 months (Yes or No)
- Surgery for UC (Yes or No), including the number of surgeries among those with surgery for UC = Yes
- Hospitalizations for UC (Yes or No), including the number of hospitalizations
- Naïve to biologic or JAK inhibitor therapy (Yes or No) Reported (used for stratification at randomization)
- Naïve to biologic or JAK inhibitor therapy (Yes or No) Actual (Category of Treatment reported on the Prior Treatment for Ulcerative Colitis eCRF)
- Baseline corticosteroid use (Yes or No) Reported (used for stratification at randomization)
- Baseline corticosteroid use (Yes or No) Actual (Category of Treatment reported on the Prior Treatment for Ulcerative Colitis eCRF)

Document: \quintiles.net\enterprise\Apps\sasdata\SASb\SAS\Arena\APD334\RZA28116\Biostatistics\Documenta

tion\SAP\503-Final SAP v2.0\APD334-203\_SAP\_Final v2.0-20231120\_clean.docx

Author: PPD Version Number: 2.0

Version Date: 20Nov2023

Template No.: CS\_TP\_BS016 Revision 7 Reference: CS\_WI\_BS005

Effective Date: 01Nov2021

Page 30 of 70

- Baseline MMS group (4 to 6, 7 to 9) Reported (used for stratification at randomization)
- Baseline MMS group (4 to 6, 7 to 9, and 5 to 9) Actual (scores reported on the Mayo Clinic Score eCRF)
- Naïve to biologic or JAK inhibitor therapy Difference between the Reported and the Actual
- Baseline corticosteroid use (Yes or No) Difference between the Reported and the Actual
- Baseline MMS group (4 to 6, 7 to 9) Difference between the Reported and the Actual
- Prior failure of oral 5-ASA only (Yes or No)
- Prior failure of anti-TNFα (Yes or No)
- Prior failure of anti-TNFα or vedolizumab (Yes or No)

Prior treatment for UC will be summarized, including category of treatment, reason for discontinuation, and estimated duration (weeks) of corticosteroid use over the last 12 months.

### 11.1. Derivations

- Duration of UC (year) = (Informed consent date Date of diagnosis by physician + 1) / 365.25
- Weight (kg) = Weight (lb) × 0.4536
- Height (cm) = Height (in) × 2.54
- Height (m) = Height (in) × 0.0254 = Height (cm) × 0.01
- BMI (kg/m^2) = Weight (kg)/Height (m)

For date of diagnosis by physician, if day is missing, then impute to 1st of the month, if day and month is missing, then impute to 1st January.

# 12. MEDICAL HISTORY

Medical history will be collected on the medical history eCRF and coded using Medical Dictionary for Regulatory Activities (MedDRA, v24.1 or higher). The version used to code medical history will be displayed in the outputs. All medical history will be summarized for the Safety Set by system organ class (SOC) and preferred term (PT).

# 13. MEDICATIONS AND NON-DRUG TREATMENT

Medications will be captured on the Concomitant Medications eCRF and coded using the World Health Organization (WHO) Drug dictionary (WHODDE01SEP2021 or higher). Refer to APPENDIX 2 for handling of partial dates for medications. In the case where it is not possible to define a medication as prior or concomitant, the

Document: \quintiles.net\enterprise\Apps\sasdata\SASb\SAS\Arena\APD334\RZA28116\Biostatistics\Documenta

tion\SAP\503-Final SAP v2.0\APD334-203 SAP Final v2.0-20231120 clean.docx

Author: PPD Version Number: 2.0

Version Date: 20Nov2023

Template No.: CS TP BS016 Revision 7 Reference: CS WI BS005

Effective Date: 01Nov2021

Page 31 of 70

medication will be classified by the worst case (ie, concomitant).

- 'Prior' medications are medications which started and stopped prior to the first dose of study treatment
- 'Concomitant' medications are medications which started prior to, on or after the first dose of study treatment AND ended on or after the date of first dose of study treatment or were ongoing at the end of the study

Concomitant medications will be summarized by Anatomical Therapeutic Chemical (ATC) Level 2 and Preferred Drug name for the Safety Set. Concomitant medications being used for UC will be flagged as such on the Concomitant Medications eCRF and summarized by ATC Level 2 and Preferred Drug name for the Safety Set.

Non-drug treatment will be captured on the Concomitant Non-Drug Treatment eCRF and coded using MedDRA version 24.1 or higher. A listing will be provided for Safety Set.

#### STUDY TREATMENT EXPOSURE 14

The date of first and last study treatment administration will be taken from the Day 1 On Site Dosing Administration eCRF and the End of Study eCRF, respectively. Interruptions, compliance, and dose changes are not taken into account for duration of exposure. Exposure to study treatment in weeks will be summarized for the Safety Set.

Dose interruptions will be recorded on the Dosing Administration eCRF, and overdose will be recorded on the Overdose eCRF. The frequency and percentage of participants who had at least 1 dose interruption, who had at least 1 dose interruption of > 7 days, who had at least 1 dose interruption of > 14 days, who had 1 overdose, and who had > 1 overdose will be summarized.

### 14.1. Derivations

Duration of exposure (weeks) = (date of last study treatment administration – date of first study treatment administration + 1) / 7. For participants with missing Date of Last Dose on the End of Study eCRF, their date of last study treatment administration will be imputed by the last date of all Dosing Administration start/end dates eCRF recorded

#### 15. STUDY TREATMENT COMPLIANCE

The time on study (weeks), total subject-years on study, total treatment exposure (weeks), total subject-years of exposure, total number of tablets expected, total number of tablets taken, total number of tablets missed, overall

\\quintiles.net\enterprise\Apps\sasdata\SASb\SAS\Arena\APD334\RZA28116\Biostatistics\Documenta Document:

tion\SAP\503-Final SAP v2.0\APD334-203\_SAP\_Final v2.0-20231120\_clean.docx

2.0 Author: Version Number: PPD

> Version Date: 20Nov2023

Template No.: CS\_TP\_BS016 Revision 7 Reference: CS\_WI\_BS005

Effective Date: 01Nov2021

Page 32 of 70

compliance with study treatment, and frequency and percentage of study treatment exposure category (< 4 weeks,  $\geq$  4 and < 8 weeks,  $\geq$  8 and < 12 weeks and  $\geq$  12 weeks) and participants with overall compliance of < 80% or > 120% will be summarized for the Safety Set.

#### 15.1. Derivations

Compliance with study treatment is based on the Drug Accountability eCRF and will be calculated as the total number of tablets taken (total dispensed – total returned) divided by the number of tablets expected during the Treatment Period, expressed as a percentage, refer to calculations below.

The total number of tablets expected is defined as the number of tablets that a subject is expected to have taken between their first and last study treatment administration and is numerically identical to the subject's overall study treatment exposure, since the medication is to be taken once daily. On any site visit day, the medication is to be held and taken at the site, after all predose assessments have been completed. For example, if a subject took their last dose of study treatment on Day 60 and returned to the site on Day 78 to return the study treatment bottle, then the total number of tablets expected would be 60, not 77.

 Total number of tablets expected = (date of last study treatment administration – date of first study treatment administration + 1) (days) × 1 (tablet / day)

For all bottles not returned, it will be assumed that all dispensed tablets were taken. For each subject, if a high percentage (> 25%) of bottles were not returned by a subject, additional analyses may be done where bottles not returned are excluded from the overall compliance calculation for that subject. In such analysis, the date of last dose or the date of last bottle return, whichever is earlier, will be used as the "date of last dose" in the calculation above.

Both scheduled and unscheduled study treatment dispensations will be used in the compliance calculation. Overall compliance calculations will be performed for the 12-Week Treatment Period and will be used in determining inclusion/exclusion of participants in the respective Per Protocol Set.

Other derivations are shown below:

- Time on study (weeks) is calculated as ("Date of Completion/Termination of Study" on the eCRF Page "End of Study" – informed consent date + 1)/7.
- Total subject-years on study is calculated as the sum of duration of time on study (days) across all subjects divided by 365.25.
- Exposure (weeks) is calculated as (end date of study treatment start date of study treatment + 1)/7.

Document: \quintiles.net\enterprise\Apps\sasdata\SASb\SAS\Arena\APD334\RZA28116\Biostatistics\Documenta

tion\SAP\503-Final SAP v2.0\APD334-203 SAP Final v2.0-20231120 clean.docx

Author: PPD Version Number: 2.0

Version Date: 20Nov2023

Template No.: CS TP BS016 Revision 7 Reference: CS WI BS005

Effective Date: 01Nov2021

Page 33 of 70

- Total subject-years of exposure is calculated as the sum of duration of treatment exposure (days) across all subjects divided by 365.25.
- Tablets missed is calculated as (the number of tablets expected the number of tablets taken) and can be negative if subject has taken more than expected number of tablets.

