6.6. Treatment Compliance

It is the Investigator's responsibility to ensure that participants are correctly instructed on how to take their study treatment and that each participant is compliant with their assigned regimen. The study treatment should be dispensed by the Investigator, or by a qualified individual under the Investigator's supervision. Participants will record the time of their dose each day in the participant eDiary. An up-to-date treatment inventory/dispensing record must be maintained as described in Section 8.4.

Overall treatment compliance will be calculated at the end of study treatment and tabletcounts < 80% or > 120% of the expected value at the end of treatment should be documented as a protocol deviation. If there is a discrepancy between the tablet count and the participant's compliance per the eDiary between visits, or if overall treatment compliance is <80% or >120% between visits, it should be discussed with the participant to improve compliance and the discussion should be noted in the source documents.

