If the ALC is confirmed below the 200 cells/ μ L limit, study treatment should be interrupted and should not be reinitiated if the ALC remains below this threshold. In this situation, the unblinded Medical Monitor will notify the Investigator and provide instructions on additional actions that the Investigator may need to take. When there is at least one measurement of ALC < 200 cells/ μ L, blinded values may be released to treating physicians and Investigators as deemed medically

necessary to monitor infection and/or aid in diagnostic work-up as clinically indicated, and/or as a tool to assess the effectiveness of therapeutic interventions for an infection. Investigators will repeat CBC with differentials weekly until ALC > 500 cells/ μ L.

Re-initiation of the study treatment can only be considered when ALC > 500 cells/ μ L.

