^w To be read by a blinded central reader. Proctosigmoidoscopy/colonoscopy should be performed prior to randomization to allow central reader review (may take approximately 5 to 12 days) and confirmation of eligibility ([Section 9.8.1.1](#)). If the ET visit is within 4 weeks of the last sigmoidoscopy and biopsy, these procedures do not need to be repeated.

^x Pharmacokinetic blood samples are to be collected predose, 4 hours (\pm 15 minutes) postdose on Week 0/Day 1 (PK sample to be collected after 12lead ECG), and predose (for trough level, within the 60minute period prior to dosing) on all other indicated days. A PK sample should be taken, if possible, at the time of any SAE or adverse event leading to study treatment discontinuation. In addition, for participants not enrolling into the APD334-303 study, a blood sample for PK should be drawn at the 2-Week and 4-Week Follow-Up visits. For all PK blood draws, the time of the last dose should be documented. For participants enrolling in the OLE at the Week 12 visit, the PK sample can be collected as part of the OLE.

^y Blood samples for biomarkers should be collected on the indicated days prior to the daily dosing as applicable.

^z Biomarkers will be collected at Week 12 but will not be collected at ET.

^{aa} All concomitant medications and procedures should be collected from Day 1 (predose) through the safety reporting period ([Section 6.7](#)).

^{bb} Study treatment should be dispensed at Week 12 if the participant continues treatment in APD334-303 OLE. Additionally, participants who consent and are eligible for the APD334-303 OLE study but do not enter the OLE on the same day as the Week 12 visit may also be dispensed study treatment.

^{cc} On days with scheduled study visits, participants should wait to take their study treatment until after blood draws for PK and after all pre-dose assessments and procedures have been completed.

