## 5.4. Per Protocol Set (PPS)

The Per Protocol Set will consist of all participants in the FAS who adhere to the protocol. This set will be used in supplementary analyses of the primary endpoints to evaluate the influence of major protocol violators and protocol deviators on the primary results.

Participants may be excluded from the PPS if they violate the eligibility criteria or significantly deviate from the study plan, including, but not limited to:

Overall study treatment noncompliance (< 80 or > 120%)

Document: \quintiles.net\enterprise\Apps\sasdata\SASb\SAS\Arena\APD334\RZA28116\Biostatistics\Documenta

tion\SAP\503-Final SAP v2.0\APD334-203\_SAP\_Final v2.0-20231120\_clean.docx

Author: PPD Version Number: 2.0

Version Date: 20Nov2023

Template No.: CS\_TP\_BS016 Revision 7 Reference: CS\_WI\_BS005

Effective Date: 01Nov2021

Page 20 of 70

- Receive incorrect study treatment for > 7 days
- Use rescue medication (new or dose increase from the highest dose of background treatment for UC received during Screening) or undergo rescue medical procedure that may affect efficacy endpoint at Week 12
- Miss Week 12 endoscopic score (ES) in prespecified analysis window (per Section 6.4) for reasons other than
   UC flare or discontinued due to disease worsening or lack of efficacy

Refer to APPENDIX 5 for the definition of rescue therapies (medication and medical procedures). All protocol deviations will be reviewed in addition to the programmable deviations (eg, study treatment noncompliance) to determine if any deviation is significant enough to exclude a subject from the Per Protocol Set. All exclusion flags will be finalized before study unblinding. Participants excluded from Per Protocol Set will be listed along with the reason category above. Participants will be summarized by treatment to which they were randomized, regardless of treatment actually received.

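### SAP 15.1 counts every tablet in an unreturned bottle as taken but stops expected tablets at the last dose, so correct dosing can be reported as above 120% compliance

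*SAP*

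**What the plan says.** SAP 15.1 defines compliance as tablets taken (dispensed minus returned) over tablets expected. For bottles that never come back it states: "For all bottles not returned, it will be assumed that all dispensed tablets were taken". It also states: "Both scheduled and unscheduled study treatment dispensations will be used in the compliance calculation".

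Expected tablets are the days from first to last dose inclusive, at one tablet a day, a count that "is numerically identical to the subject's overall study treatment exposure". The last dose date comes from the End of Study form, and SAP 14 says interruptions do not shorten exposure.

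The result has two uses. SAP 15 tabulates overall compliance, and the share of participants outside 80 to 120%, for the Safety Set. SAP 15.1 also sends it to Per Protocol membership, where SAP 5.4 lists as a possible ground for exclusion "Overall study treatment noncompliance (< 80 or > 120" per cent.

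SAP 15.1 has a fallback: if more than 25% of a participant's bottles are missing, further analyses leaving those bottles out may be run.

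A second dose record exists. Protocol 6.6 says: "Participants will record the time of their dose each day in the participant eDiary". The SAP 15.1 formula does not use it.

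**The concern.** The two halves of the ratio stop at different times. The denominator ends with the last dose. The numerator, for a bottle that is not returned, includes tablets that could only have been taken after that dose. Someone who dosed exactly as instructed can then appear to have taken far more than one tablet a day.

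The people most exposed are those who stop early and do not bring the last bottle back. That group may include participants who stopped for lack of efficacy. SAP 5.4 exempts them from the exclusion for a missing Week 12 endoscopic score, and SAP 16.1.2 lets them stay in the Per Protocol Set as nonresponders provided they breach no other criterion. A false reading above 120% can be that other criterion, so the loss from the set can be linked to outcome.

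**Working it through.** **Inputs.** Dispensing at Day 1 and Weeks 2, 4 and 8 (Protocol Table 6), giving intervals of 14, 14, 28 and 28 days; one tablet a day; limits of 80% and 120%. Two assumptions are needed because the documents are silent: one bottle per dispensing visit, and 28 to 40 tablets per bottle. The ±3-day visit window makes 31 to 34 plausible for a four-week supply.

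**The plan's own figure.** In the SAP 15.1 example the last dose is on Day 60: expected = 60 − 1 + 1 = 60. This reproduces the stated 60.

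**Early stopper, all doses taken, Week 8 bottle (B tablets) not returned.** True intake to Day 60 is 56 + 4 = 60. Reported compliance is (56 + B)/60:

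- B = 28: 84/60 = 140%
- B = 31: 87/60 = 145%
- B = 34: 90/60 = 150%

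With B = 28 the figure falls as the stop comes later: 84/65 = 129.2%, and 84/70 = 120.0%, which is no longer above the limit.

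**Completer, 84 doses taken, one bottle lost.**

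- From a 14-day interval, (84 + B − 14)/84: B = 28 gives 116.7%, B = 30 gives 119.0%, B = 31 gives 120.2%, B = 34 gives 123.8%. The breach starts at 31 tablets.
- From a 28-day interval, (84 + B − 28)/84: 100.0% at B = 28 and 114.3% at B = 40. No breach.

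**Error in the other direction.** If 17 doses are skipped after Week 8 and that 28-tablet bottle is lost, the report is (56 + 28)/84 = 100%; the truth is 67/84 = 79.8%.

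**Does the fallback catch it?** One bottle of four is 25%, not more than 25%, so the Day 60 case does not trigger it. A participant who stops at Day 40 without returning the Week 4 bottle has one of three missing (33%). The main figure is (28 + 28)/40 = 140%. The fallback, if run with the last return on Day 29, gives 28/29 = 96.6%, which is sensible. If a completer's Week 2 and Week 4 bottles are missing and the Week 8 bottle is returned, the fallback drops their tablets but keeps 84 expected days: (14 + 28)/84 = 50% with perfect dosing. The SAP does not say which figure governs when the two differ.

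**With eDiary doses for the lost bottle.** Day 60 case: (56 + 4)/60 = 100%. Completer with a lost 14-day bottle: (70 + 14)/84 = 100%.

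**Interruptions, a separate matter.** Otherwise adherent completers who restart after a hold score (84 − h)/84: 83.3% for 14 days, 81.0% for 16 and 79.8% for 17.

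**The case against.** Several points limit the matter, and most of them stand.

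- Exclusion is not automatic. SAP 5.4 says participants may be excluded, after all deviations are reviewed and with flags fixed before unblinding. A reviewer could recognise a lost bottle. The SAP gives no rule for that case, however, and the Safety Set table is not described as subject to such a review.
- In the SAP's Day 60 example the bottle is returned; the 140% case changes that.
- Early stoppers attend a termination visit within 7 days of the last dose (Protocol 5.1), so by about Day 67 here, while the Week 12 endoscopy window opens on Day 66 (SAP Table 2). Many will have no endoscopic score in the window and may be excluded for that alone. The exception is stopping for flare, worsening or lack of efficacy, which is where the compliance artefact still matters.
- Bottles are collected at each visit (Protocol 8.4) and discrepancies with the eDiary are discussed with the participant (Protocol 6.6). This should make lost bottles uncommon; the documents give no rate.

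A reader might infer two stronger claims that the documents do not support. First, because the Protocol Table 6 notes say "Study treatment should be dispensed at Week 12 if the participant continues treatment in APD334-303 OLE", one might add that bottle and obtain (84 + 28)/84 = 133% for extension entrants. SAP 15.1 limits overall compliance to the 12-Week Treatment Period, and nothing places extension supply in the numerator. Second, one might say that every hold the protocol orders is scored as missed tablets. Only holds followed by a restart are, because expected tablets end at the last dose, and a completer needs at least 17 such days to fall below 80%. Whether someone without drug for that long belongs in a Per Protocol Set is a legitimate choice either way.

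**Conclusion.** The rule as written gives a wrong compliance figure in identifiable cases. The clearest is the early stopper with an unreturned last bottle: 140% for perfect dosing to Day 60, on the smallest supply that covers the interval. The completer case is weaker, since it needs a two-week bottle of 31 or more tablets. Both rest on one bottle per dispensing visit.

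The consequence is limited to the Safety Set compliance table and the Per Protocol rerun of the primary endpoint, which is supplementary. SAP 6.5 plans no statistical test, and the primary analysis in the Full Analysis Set does not use compliance. As a guide to size, the planned 31.5% remission in 32 participants is about 10 of 32 (31.3%); wrongly removing one nonresponder gives 10/31 = 32.3%, about one percentage point, and somewhat more in the smaller groups now expected. How many participants would be affected cannot be told from the documents. The correction is worth making because it is cheap and because the participants at risk of removal can be nonresponders whom the plan otherwise allows to stay.

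**What to change.** In SAP 15.1, replace the assumption for unreturned bottles. Count the doses recorded in the eDiary from the bottle's dispensing date to the earlier of the next dispensing or the last dose, never more than the days in that interval. Apply the 80 to 120% screen in SAP 5.4 to this figure, and say that it governs.

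Optionally, show compliance with and without the interruption days recorded on the Dosing Administration form, and state before unblinding which version the Per Protocol screen uses. This concerns the calculation only, not when treatment is held.

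The cost is SAP wording and reprogramming on data already collected. The drawback is that eDiary entries are self-reported, and a day without an entry would count as not taken, so the new figure can err low.
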